For immunocytochemistry and for protein expression analysis, the spots of the membranes will be cut and placed in 24-well plates. Each spot will be hydrated with Tris Buffered Saline (TBS) for 10 minutes. Cells will be permeabilized with 0.2 percent Triton X-100 TBS for 5 min at room temperature. After a further TBS wash, the membranes will be incubated for 15 minutes in the dark and at room temperature with a 3 percent solution of hydrogen peroxide, and washed again with TBS. Then the antibodies to be screened will be applied to the spots and incubated for one hour. For the negative control, the primary antibody will be omitted. The development will be done with Dual long HRP system (Dako™) and Diaminobenzidine chromium 3,3 '(DAB) (Dako™). For reading, the spots will be stained with hematoxylin for 1 minute and adhered to the slides with aqueous mount medium. The CTC will be characterized according to the following criteria: nuclear size equal to or greater than 16µm, nuclear contour irregularity, presence of visible cytoplasm, high nucleus-cytoplasm ratio (> 0.8), as described by KREBS et al .19 When any of the criteria described are missing, the cells will be classified as atypical. The results will be given in CTC number per mL of blood.

Methodology for the PET-CT scan with Gallium-68 for the detection of somatostatin receptors

The PET-CT scan with gallium 68 to investigate somatostatin receptors will be performed using the Gemini PET-CT equipment (PET-CT-Dedicated) after administration of 0.1mCi of ⁶⁸Ga-DOTATATE, as already performed in the routine of AC Camargo as a staging method for NET. The images will be started in the minimum interval of 30 minutes and maximum of 60 minutes after the dose. CT - Helicoidal: contiguous anatomical tomographic sections 2.5 mm thick (without intravenous contrast) throughout the body (cranial, thoracic, abdominal, pelvic and lower limb segments). The Standard Uptake Value (SUV) calculation or standard capture value performed for clinically significant areas.

Study population:

Elegibility:

Research participants will be recruited from Clinical Oncology outpatient clinics and must meet all criteria below Inclusion and none of Exclusion:

Inclusion criteria

- Age greater than or equal to 18 years

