- Histological diagnosis of well differentiated NET (typical and atypical lung carcinoids, NET G1, NET G2 of all gastroenteropancreatic sites and pancreatic NET G3 according to WHO 2017 classification) 20 advanced / metastatic, inoperable, with no possibility of curative treatment
- Immunohistochemical expression ≥ 1 percent for estrogen and / or progesterone receptor
- Disease with radiological progression (at least 10 percent tumor volume growth) in the last 12 months before day 1 cycle 1.
- No possibility of established treatments due to lack of access, risk of toxicities or without clinical indication. Patients who meet criteria for watchful waiting (low-dose disease and non-functioning NET) may be included.

- Measurable disease
- ECOG performance scale 0 to 2.
- Adequate organ function as defined by the following criteria:
 - serum aspartate aminotransferase (AST), serum alanine aminotransferase (ALT) \leq 2.5 times the upper limit of local laboratory normality (LSN-LL);
 - Total serum bilirubin \leq 2.0 x ULN-LL;
 - Absolute neutrophil count \geq 1,500 / mm³;
 - Platelet count \geq 80,000 / mm³;
 - Hemoglobin \geq 9.0 g / dL;
 - Estimated creatinine clearance by the MDRD equation \geq 30ml / min
 - Albumin \geq 3.5 g / dL;
 - INR \leq 1.5
 - Term of free and informed consent signed by the patient or legal representative.

Exclusion criteria

- Patients already on tamoxifen.
- Patients with aggressive disease requiring cytotoxic therapy or locoregional therapies (eg hepatic embolization)
- A history of serious clinical or psychiatric illness that, by clinical judgment, may involve participation risk in this study
- Patients participating in other protocols with experimental drugs.
- Patients with oral food difficulties.
- Patients who underwent major recent surgery less than 4 weeks previously.
- Patients receiving chemotherapy or other oncologic therapy for less than 3 weeks.

- Patients who use oral anticoagulation
- Previous history of deep vein thrombosis or pulmonary embolism in the last 12 months.
- Pregnant or lactating patients.
- Patients with postmenopausal vaginal bleeding with no defined etiology.
- Patients with breast cancer who need to use tamoxifen for this neoplasm
- Another synchronous neoplasm that requires systemic treatment

Treatment:

Tamoxifen:

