The main adverse effects of tamoxifen are hot flushes, dry skin, nausea, vaginal discharge, fatigue and changes in the menstrual cycle. Rarely, but importantly may be associated with retinal changes, hepatotoxicity, hematological changes, thromboembolic phenomena and endometrial neoplasia. Given the teratogenic potential, women of childbearing potential should undertake contraceptive measures. Such medication should be contraindicated in cases of hypersensitivity to tamoxifen or any component of the formulation, concomitant use of coumarins and history of deep vein thrombosis or pulmonary embolism.

Administration

The treatment to be used will be tamoxifen 20mg VO once daily with a glass of water. In cases of vomiting occurring after 1 hour of taking or when a dose is missed, the patient will be instructed to skip this dose and not compensate for the next dose. Each cycle will be defined for 42 days (6 weeks).

Aderence:

The dispensation of tamoxifen will be made by the research pharmacy of the institution. Approximately 20 mg tamoxifen tablets will be given to each patient until the next return to the oncologist (see TABLE 1).

To assess adherence to treatment we will require patients to bring the blisters at each visit and at the time of discontinuation of treatment.

Dose reduction:

Dose interruption or reduction will be allowed in case of any toxicity of degree equal to or greater than 3 or intolerable grade 2 toxicity, as shown in the table below.

TABLE 3 - Dose adjustment according to toxicity

Study drug and dose	Tamoxifen 20mg orally once daily
Haematological or non-haematological toxicity grade \geq 3 or grade 2 intolerable.	Suspend therapy until recovery of the condition (with weekly evaluation by the investigator until the end of the recovery). When improvement of the picture (grade 1 toxicity), restart with tamoxifen 10mg tablet orally daily If there is no improvement in clinical status within 3 weeks (persisting with grade 3 or grade 2 intolerable toxicity) or patient does not tolerate the 10 mg / day dose, the patient will be excluded from the study for unacceptable toxicity.
Haematological or non-haematological toxicity <grade 2	No dose reduction will be performed for tolerable grade 1/2 toxicities.

Security Assessment

Baseline Assessment:

After signing the informed consent form, patients will be submitted to baseline evaluation to assess the patient's eligibility (see TABLE 1):

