Descriptive statistics will be used to report the results of categorical and continuous variables. The time-to-event variables will be reported in medians and Kaplan Meyer curves. The degrees of toxicity will be tabulated. The number of patients discontinuing treatment due to toxicity will be presented.

Efficacy and toxicity analyzes will be performed by intention to treat. Patients receiving at least one dose of tamoxifen will be evaluated for toxicity and efficacy.

Inferential analyzes of the primary outcome according to primary site and IHC HR expression intensity will be conducted to depend on the number of cases per subgroup; if possible, these analyzes will be performed with the chi-square test. The analyzes of intensity of uptake intensity to PET-CT gallium-68 will be with paired T-test. The CTC analysis will be presented in a descriptive way.

Sample Size Calculation

To calculate the sample size, we considered the disease control rate H0 at 6 months of 50 percent (placebo arm result of the phase III studies) 5,23 and H1 as a 6 months disease control rate of 70 percent. A 10 percent bitailed type I error was considered, 80 percent power loss and 30 percent follow up loss. With these calculations, the sample number will be 22 patients.

Recruitment and Study Duration

At the AC Camargo Cancer Center, 30 patients with advanced NET are treated annually. Therefore, considering the patients already under treatment and the possible candidates without previous treatment and that out of every 10 patients, N = 4 will meet eligibility criteria (NETs with positive HR), we estimate to recruit the study population in a maximum period of 3 years and have the first full evaluation in 3 ½ years.

Ethical Considerations

The study will be conducted in accordance with the protocol, Good Clinical Practice guidelines of the International Conference on Harmonization (ICH GCP) and applicable local laws and regulatory requirements. The Free and Informed Consent Term (ICF) must be in accordance with ICH GCP guidelines, local regulatory regulations, and legal requirements. See Appendix 2 for ICF.

The investigator should ensure that each study patient, or his / her legal representative, is fully informed about the nature and objectives of the study and

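### A DVT or PE more than 12 months old does not exclude a patient, although the protocol itself calls tamoxifen contraindicated after any such event

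*Combined protocol and SAP*

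**What the plan says.** Under Study population, the eligibility rule is that participants "must meet all criteria below Inclusion and none of Exclusion". The Exclusion criteria list contains one item on thromboembolic history: "Previous history of deep vein thrombosis or pulmonary embolism in the last 12 months". Two other items on the list bear on the same patients: "Patients who use oral anticoagulation" and "A history of serious clinical or psychiatric illness that, by clinical judgment, may involve participation risk in this study".

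The Tamoxifen section under Treatment describes the drug. Among its uncommon but important risks it names "hematological changes, thromboembolic phenomena and endometrial neoplasia". It then states the contraindications: "Such medication should be contraindicated in cases of hypersensitivity to tamoxifen or any component of the formulation", followed in the same sentence by "concomitant use of coumarins and history of deep vein thrombosis or pulmonary embolism". No time limit is attached to the DVT or PE item.

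The Study design section says that, for a patient who meets the clinical and radiological criteria and has consented, a positive hormone-receptor result completes eligibility and tamoxifen is then given.

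**The concern.** The exclusion list and the drug section give different answers for the same patient. By the contraindication sentence, a patient with a PE three years ago should not receive tamoxifen. By the exclusion list, that patient passes the only criterion that names the condition. No section says why events older than 12 months are acceptable.

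What is at stake is participant safety. Tamoxifen is taken daily until progression, unacceptable toxicity or withdrawal of consent, so exposure may be long. The trial may also enrol patients who could otherwise simply be observed. For someone with an older event, protection rests on the individual investigator's judgment, with no stated criterion behind it.

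**Working it through.** There is no figure in the plan to reproduce. The check is a comparison of texts, followed by a sense of scale.

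**Step 1: the contraindication sentence against the exclusion list.**

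| Contraindication (Tamoxifen section) | Matching exclusion | How it was carried over |
|---|---|---|
| Concomitant coumarins | Any oral anticoagulation | More broadly |
| History of DVT or PE, no time limit | DVT or PE in the last 12 months | More narrowly, no reason given |

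**Step 2: can another rule catch an older event?** Take a patient whose DVT or PE was more than 12 months ago.

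- The oral anticoagulation exclusion removes the patient only if still on treatment. Someone who has finished a course passes.
- The serious-illness exclusion depends on clinical judgment and does not name DVT or PE. An investigator who sees an explicit 12-month rule beside it could reasonably infer that older events are allowed.
- The Baseline Assessment records past as well as current illnesses, so the event would probably be known. No rule says what must follow.
- The section on other concomitant medications discusses anticoagulant interactions and adds no restriction on DVT or PE history.
- Table 3 has no rule specific to thromboembolism. It allows a restart at 10 mg once a grade 3 or higher toxicity has improved to grade 1.

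So a patient with an older event, off anticoagulants and not excluded on judgment, meets no exclusion and still falls under the contraindication.

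**Step 3: how often the gap might be used.** The documents give no share of candidates with an older DVT or PE. Let p be that share among otherwise eligible candidates. The values below are assumptions, and patients are treated as independent. With n = 22 (Sample Size Calculation):

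- chance of at least one such patient = 1 − (1 − p)^22
- expected number = 22p

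| Assumed p | 1 − (1 − p)^22 | 22p |
|---|---|---|
| 1% | 19.8% | 0.22 |
| 2% | 35.9% | 0.44 |
| 5% | 67.6% | 1.10 |

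**Step 4: effect of a wider exclusion on recruitment.** Recruitment and Study Duration states that "30 patients with advanced NET are treated annually", that 4 in 10 are expected to be eligible, and that recruitment takes at most 3 years.

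- Projected candidates: 30 × 0.4 × 3 = 36
- Margin over the 22 needed: 36 − 22 = 14
- Candidates lost at p = 1%, 2%, 5%: 36p = 0.36, 0.72, 1.80

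**The case against.** The strongest reply is that the window is a deliberate threshold. On this view the Tamoxifen section is a general drug summary and the exclusion list sets the trial's own risk-benefit limit, for patients who mostly lack access to established treatment or cannot take it. Elsewhere the protocol grades the anticoagulant interaction as only a moderate contraindication, so the word need not be absolute. It can also be said that meeting the lists is necessary for enrolment but need not be sufficient. Hypersensitivity is contraindicated yet missing from the exclusions, which suggests that the drug section is meant to apply alongside the list. A prescriber who reads the whole protocol would then still meet the warning, with the medical history in hand.

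Part of this stands. The window may have been intended, the baseline history and the regular safety visits do narrow the gap, and the assumed shares in Step 3 carry no evidential weight.

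The rest does not. The graded wording concerns anticoagulants, whose oral forms the exclusion list bars outright. It says nothing about thromboembolic history. The Study design section moves directly from completed eligibility to treatment, so the contraindication text is not a further check before dosing. The history reveals an older event without requiring anyone to act on it. If the window was intended, the protocol still gives no reason for it and leaves the contraindication unqualified.

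**Conclusion.** The concern holds. The written criteria admit a patient with a DVT or PE more than 12 months old who is off oral anticoagulants and not excluded on judgment, although the protocol's own drug section says tamoxifen should be contraindicated for that patient. This conclusion rests on the text alone and needs no assumption about prevalence.

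The likely number of patients is small: about 0.2 to 1.1 of 22 if the share is 1% to 5%, and possibly none. No excess event rate can be derived from the documents. The point should be corrected on safety grounds, and it has no bearing on the trial's efficacy conclusions.

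**What to change.** Delete the 12-month limit from the DVT/PE item in the Exclusion criteria, so that any previous DVT or PE excludes. The list then agrees with the Tamoxifen section.

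The cost is one phrase in an amendment and perhaps a few candidates: 0.4 to 1.8 of the projected 36 at the assumed shares, against a margin of 14. The 36 is rough. The 4-in-10 figure is tied to receptor positivity, refusals and other exclusions are not taken off, and the protocol also counts on patients already under treatment.

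If the sponsor wants to keep a window, the alternative is to justify it in the protocol and qualify the contraindication sentence to match. Nothing in the present documents supplies that justification, so deletion is the better course.

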- Within 21 days of the first dose of treatment: investigation of the immunohistochemical expression of RH in the paraffin-shaped tumor material. If expression \geq 1 percent, eligibility is confirmed and the following procedures are:

- Within 3 days of day 1 cycle 1: Medical history, including diagnosis and previous treatments, history of other diseases (active and resolved), medications in use and general demographic data. Complete physical examination, ECOG (PS) performance index, body weight and height, and vital signs.
- Laboratory tests: blood count, urea, creatinine, ALT, AST, total bilirubin, sodium, potassium, INR and albumin and pregnancy test for women of childbearing age will be performed within 3 days of the first dose of treatment; these patients will be directed to contraception.
- It will be accepted that baseline imaging has been performed within 8 weeks of the first dose of treatment: Computed tomography (or nuclear magnetic resonance, if applicable) of the abdomen, pelvis and chest.
- All of these above exams are already part of the routine in treating NET at the AC Camargo Cancer Center.

Security Assessment at Week 3:

Adherence and presence of adverse events will be assessed at this time (see Safety Assessment). Will be allowed window of +/- 5 days

Safety evaluation on other weeks:

At each medical appointment, the adverse effects and toxicity related to the treatment will be evaluated by means of anamnesis, physical examination and laboratory evaluation, as follows:

- Complete physical examination, measurement of vital signs, measurement of weight and height, ECOG, use of concomitant medications.
- Evaluation of adherence to treatment.
- Evaluation of adverse events

- Laboratory evaluation: blood count, urea, creatinine, ALT, AST, total bilirubin, sodium, potassium, and others, if clinically indicated.

To grade toxicities, we will use CTCAE 5.0 criteria. Patients who present intolerable grade 2 toxicity or grade 3 that the investigator judges to be related to tamoxifen will have the reduced dose of treatment (see TABLE 3) and will be conducted as previously discussed. All adverse effects will be graded and evaluated whether or not they are related to treatment.

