If there is no CTCAE 5.0 classification for an adverse event, the severity degree of mild, moderate, severe and life threatening will be used. Adverse event monitoring will be performed at Week 3 after initiation of treatment (window - / + 3 days) and at each return with the oncologist every 6 weeks (window - / + 3 days). Monitoring of adverse events should be continued for at least 4 weeks after the last dose of study treatment.

An adverse event for the purposes of this protocol is the appearance of (or worsening of the pre-existing) signal (s), symptom (s) or undesirable medical condition (s) occurring after signature of free and informed consent, even if the event is not considered to be related to the study drug (s). The occurrence of adverse events should be obtained through indirect questions asked to the patient at each visit during the study. Adverse events may also be detected when reported voluntarily by the patient during or between visits or by physical examination, laboratory examination or other evaluation.

Whenever possible, each adverse event should be evaluated to determine:

1. Severity (mild, moderate, severe and life threatening) or (CTCAE grade 5.0)
2. Their relationship to each study drug (suspected / suspected)
3. Their duration (starting dates and final or continuing in the final exam)
4. Conduct adopted (no dosage adopted, dosage of study drug adjusted / temporarily discontinued, study drug permanently discontinued as a result of said adverse event, concomitant medication given, non-medicated therapy, prolonged hospitalization / hospitalization).

Patients requiring hospitalization should be immediately identified by the study investigators who monitor all patients.

Treatment suspension criteria:

Patients can discontinue study treatment for one or more of the following reasons:

- Progression of the disease (documented by images and defined by RECIST 1.1 criteria)

Clinical progression, based on the evaluation of the investigator

- Death.
- Adverse event
- Withdrawal of consent by the patient.
- Need for new cancer therapy and / or surgery.

Efficacy and Follow-Up Assessment

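### Table 3's generic toxicity rule has no exception for deep vein thrombosis or pulmonary embolism, so read literally it conflicts with the protocol's own contraindication

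*Combined protocol and SAP*

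**What the plan says.** Five places in the protocol bear on this point.

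- **Treatment, Tamoxifen.** Thromboembolism is named among the drug's rare but important harms. The contraindications listed there include "concomitant use of coumarins and history of deep vein thrombosis or pulmonary embolism". No time limit is attached.
- **Exclusion criteria.** A patient is barred at entry for "Previous history of deep vein thrombosis or pulmonary embolism in the last 12 months". Use of oral anticoagulation is a separate exclusion.
- **Dose reduction and Table 3.** The lead-in is permissive: "Dose interruption or reduction will be allowed in case of any toxicity" of grade 3 or higher, or intolerable grade 2. For those events the table says to hold treatment and then: "When improvement of the picture (grade 1 toxicity), restart with tamoxifen 10mg tablet orally daily". If there is no improvement within 3 weeks, or 10 mg is not tolerated, "the patient will be excluded from the study for unacceptable toxicity". For milder events: "No dose reduction will be performed for tolerable grade 1/2 toxicities". The rows cover haematological and non-haematological toxicity alike and name no event type.
- **Safety evaluation on other weeks.** Patients with grade 3 or intolerable grade 2 toxicity judged related to tamoxifen "will have the reduced dose of treatment (see TABLE 3) and will be conducted as previously discussed".
- **Treatment suspension criteria.** "Patients can discontinue study treatment for one or more of the following reasons". The list includes adverse events in general. It does not name DVT or PE.

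**The concern.** Dose-modification tables are what site staff apply when an event occurs. Here the table treats a clot like any other toxicity: hold, wait for improvement, restart at half dose. A patient who has had a DVT or PE on study now has the history that the Tamoxifen section lists as a contraindication. The dosing instruction and the contraindication then point in opposite directions, and the protocol does not say which prevails.

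What is at stake is the safety of an individual patient: re-exposure to tamoxifen after one of the serious harms that the protocol attributes to it. The sample size, the error rates and the primary analysis are not involved.

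**Working it through.** No arithmetic applies, and the plan gives no figure to reproduce. The check takes each outcome that an on-study DVT or PE could have, applies the dosing rules, and compares the result with the contraindication.

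1. **Grade 3 or higher, or intolerable grade 2, improving to grade 1.** Table 3: hold, then restart at 10 mg daily. Contraindication: the patient now has a history of DVT or PE, so tamoxifen should not be given. The two conflict.
2. **Grade 3 or higher, or intolerable grade 2, not improving within 3 weeks, or 10 mg not tolerated.** Table 3: removal from the study. This agrees with the contraindication, but the trigger is non-recovery or intolerance, not the type of event.
3. **Tolerable grade 1 or 2.** Table 3: no dose reduction. Contraindication: as in case 1. The table does not order continuation in so many words, but it gives no reason to stop. The two conflict if the row is taken as complete.

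The next question is whether another section turns case 1 or case 3 into a required stop.

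- Safety evaluation on other weeks does not. For related grade 3 or intolerable grade 2 events it points back to Table 3.
- Treatment suspension criteria do not. The wording permits discontinuation for an adverse event without requiring it. Permanent discontinuation also appears in the adverse-event assessment items, but as one of the actions that may be recorded, not as a rule.
- The exclusion criteria do not. They apply at entry. They do show that the sponsor regards a recent clot as an unacceptable starting point.
- Other concomitant medications goes part of the way. It says that coumarins and some newer anticoagulants should be avoided during the study, and coumarin use is itself a listed contraindication. A patient given a coumarin for the clot would therefore meet a second contraindication, which narrows the room for a restart. The section does not cover every anticoagulant and does not say what to do with tamoxifen if one is needed.

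Cases 1 and 3 therefore remain open: stopping is available, but nothing in the dosing rules requires it.

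**The case against.** The strongest reply is that the contraindication already settles the matter. It is specific to the drug, has no time limit, is not confined to screening, and stands shortly before the dosing table. A careful investigator would read it as limiting a generic table. Stopping for an adverse event is expressly allowed, the lead-in to Table 3 only permits interruption or reduction, and any hold carries weekly review by the investigator. On this reading all that is missing is a cross-reference.

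Much of this stands. A reader might infer that the protocol compels re-exposure after a clot. It does not: the investigator can stop at any point. But the reply depends on the investigator overriding the table. It is also weakened by the protocol's own eligibility rule, which applies the history of DVT or PE only over the last 12 months although the contraindication has no time limit. If the contraindication is not applied in full at entry, it is not obvious that it silently overrides Table 3 later.

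A reader might also set the 12-month entry exclusion against a restart within 3 weeks on study and take that contrast as established. It rests on an assumption that a DVT or PE can be regraded to grade 1 in that time. The documents give no grade definitions for thromboembolism and no recovery times, so how readily a clot could reach the restart row cannot be verified.

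Finally, a reader might want a probability of re-exposure among the 22 planned patients. The documents give neither a clot rate nor a share of clots that would end back on tamoxifen, so any such figure would only restate its inputs.

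**Conclusion.** The point holds as an internal conflict. Table 3 and the section that refers back to it apply one rule to all toxicity. Read literally, that rule allows tamoxifen to be restarted, or continued without reduction, in a patient whom the Tamoxifen section calls contraindicated and whom the exclusion criteria would have barred had the event come shortly before entry. Other sections permit a stop, but none requires one.

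Its size in patients is unknown and probably small: the protocol describes these harms as rare, and investigators can intervene. The restart branch matters only if a clot can improve to grade 1 and the investigator follows the table rather than the contraindication. The no-reduction branch needs a clot that is graded tolerable 1 or 2. The documents do not support calling this a critical defect. It is a safety correction worth making because it is cheap and removes a contradiction about a serious, named harm.

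**What to change.** Add one line to Table 3: *On-study DVT or PE: discontinue tamoxifen permanently; the restart and no-dose-reduction rows do not apply.* Refer to that line in Safety evaluation on other weeks, and add the same event to the list under Treatment suspension criteria.

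The cost is a short amendment touching three places, with no change to the sample size, the error rates or the primary analysis. The real downside is that an occasional patient will stop tamoxifen who could have restarted or continued under the present table. The line is limited to DVT and PE because those are the events the contraindication names. Whether to extend it to other thromboembolic events is a clinical choice for the sponsor.
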